4.2. Evaluation of (pre)clinical testing

The 3D segmentation of the endobronchial tree based on pre-procedural CT, lesion segmentation, and pathway generation with the AirWaze investigational device (version 1.0) have been evaluated in a preclinical setting. Here, the first-pass navigation success was between 73 and 79% and was 100% in a second pass and overall. Fluoroscopy times were in clinically relevant timeframes. Navigation error, which is defined as the distance from the catheter tip to the bifurcation measured on the confirmatory CBCT, was another important endpoint. These errors were 2.2 ± 1.2 mm *ex vivo* and 4.9 ± 3.2 mm *in vivo* and are more accurate than results reported with ENB. In conclusion, endobronchial navigation was assessed as feasible and accurate with CBCT and AF guidance in both *ex vivo* and *in vivo* models ¹³.

In a clinical feasibility study, the AirWaze investigational device (version 1.0) was used to plan and guide the navigation procedure with CBCT and augmented fluoroscopy of the target lesion, pathway and bronchial tree (Figure 2) ¹⁴. A total of 52 subjects and 59 lesions with an average median lesion size of 19.0 mm (range 7-48 mm) were included in this study. The navigation success was 98.3% and the overall diagnostic yield was 91.4% (91.2% for lesions <20 mm). No severe adverse events related to CBCT NB with the AirWaze investigational device (version 1.0), such as pneumothorax, respiratory failure, were observed. These results are comparable with findings from the same clinical center using a combination of ENB and CBCT with AF of the target lesion for navigation bronchoscopy. These results demonstrate the safety of CBCT and AF guided biopsies of peripheral pulmonary lesions with the AirWaze investigational device (version 1.0) to obtain high diagnostic yields.

[figure not shown]

Figure 2. CBCT guidance in bronchoscopy with advanced software tools for peri-procedural planning and 3D image-guidance (AirWaze investigational device, version 1.0). After 3D segmentation of the target lesion and the bronchial tree on pre-operative CT data, the virtual pathway to the target nodule was generated (A-D). Automatic elastic registration of the pre-operative CT with intraprocedural CBCT data enabled live guidance with augmented fluoroscopy views of the airways and virtual pathway to the segmented target lesion I. Confirmation of tool-in-lesion (F).

IGT Systems	Feasibility Clinical Investigation Protocol AirWaze – easy and advanced tools for CBCT guided lung interventions	Doc ID: XCY607-130895 Rev: 04 Date: 2024-Jun-19 Page 16 of 56
-------------	--	--

4.3. Evaluation of clinical data

The AirWaze software tools enable the physician to plan, guide and confirm during navigation bronchoscopy of peripheral pulmonary nodules.

Background clinical application

This study is for subjects with peripheral pulmonary lesions suspicious of malignancy. Traditionally, there are three pathways for lung lesion diagnosis: (i) watchful waiting with CT follow-up, (ii) minimally invasive diagnostic techniques, and (iii) surgical excision with diagnostic analysis. There are two ways to obtain minimally invasive tissue diagnosis, namely via CT-guided TTNA and navigation bronchoscopy (Section 4.1). CBCT-guided navigation bronchoscopy combines navigation guidance with 3D-image confirmation of tool-in-lesion positioning. It can help guide and verify sampling in 3D in near real-time. CBCT-guided NB has proven to have a lower complication rate compared to CT-TTNA while maintaining diagnostic accuracy. However, disadvantages of CBCT-guided NB are the high cognitive load during planning and procedure, and the inherent use of radiation.

The AirWaze Investigational Device (version 1.1) with an improved user interface compared to version 1.0 has been designed to reduce the cognitive load before- and during CBCT-guided NB, and therewith improve overall navigation bronchoscopy procedure accuracy. Furthermore, dedicated low dose imaging protocols have been designed to reduce the radiation dose of intraprocedural 3D imaging (*i.e.* CBCT-FluoroSweep). The improved ease-of-use, reduced cognitive load and tailored radiation protocols for CBCT-guided interventions are anticipated to increase the overall accuracy of the procedure and help implement it in routine clinical practice across institutes fuel the adoption of CBCT-guided NB.

IGT Systems	Feasibility Clinical Investigation Protocol	Doc ID: XCY607-130895
	AirWaze – easy and advanced tools for CBCT guided lung interventions	Rev: 04 Date: 2024-Jun-19 Page 17 of 56

5. Risks and benefits of the investigational device and feasibility clinical investigation

The risk assessment process that Philips follows is in accordance with ISO14971. This will ensure that the level of risk is acceptable prior to the start of the clinical feasibility study.

Benefits

Benefits related to the investigational device compared to state-of-the-art devices are an improved ease-of-use and a reduced cognitive load for the physicians during CBCT-guided navigation bronchoscopy, while maintaining patient safety and a high diagnostic accuracy for peripheral pulmonary nodules.

Future patient benefit (= after clinical feasibility study of CBCT-FS): 3D confirmation of tool-in-lesion with CBCT-FS may result in less radiation dose compared to conventional CBCT and augmented fluoroscopy

There is a possibility that the patient may not benefit from participating in the study.

Risks

Risks related to the AirWaze investigational device 1.1 compared to state-of-the-art devices, the standard of care/procedure, is:

- As the novel AirWaze software will be evaluated by combining a CBCT with immediate FluoroSweep afterwards (with the intention that they will both give similar image information), radiation dose will be increased for staff and patient. The additional fluoroscopy level dose will have a minimal impact on the overall procedure and staff dose.
- Based on incorrect anatomical overlay information, the operator might deploy the catheter/biopsy tool inaccurately. Possible harm is:
 - Bronchial hemorrhage (E0707)
 - Pneumothorax (E0734)
 - Procedure related complications (E21)
 - Delay to treatment/therapy (F05)

The risks of participating in the clinical feasibility study with the AirWaze investigational device are illustrated in Table 3. All risks have been reduced as far as possible and individual residual risks after mitigation are all classified as acceptable, marked by the green zone in Table 3. No additional risks were identified when verifying the risk mitigation.

Anticipated adverse device effects are listed in section 15.3 Anticipated adverse device effects (including the steps that are taken to control or mitigate the risks).

Table 3. Overview of the residual risk profile of the investigational device.

Count of Residual Severity		Delta Residual Severity*				
Residual Probability of Harm (PoH) occurrence**		S0	S1	S2	S3	S4
PoH 5	≥ 10 000	0	0	0	0	0
PoH 4	1 000 - <10 000	0	0	0	0	0
PoH 3	100 - <1 000	0	0	0	0	0
PoH 2	10 - <100	2	1	6	0	0
PoH 1	<10	0	0	0	0	0
Grand Total		2	1	6	0	0

*Severity is defined according to:

S0 – Negligible: Results in Inconvenience or temporary discomfort not requiring professional medical intervention OR in customer dissatisfaction where there is no injury.

S1 – Minor: Results in injury or temporary impairment not requiring professional medical intervention

S2 – Major: Results in injury or temporary impairment requiring professional medical intervention

IGT Systems	Feasibility Clinical Investigation Protocol	Doc ID: XCY607-130895
	AirWaze – easy and advanced tools for CBCT guided lung interventions	Rev: 04 Date: 2024-Jun-19 Page 18 of 56

S3 – Critical: Results in permanent impairment OR in an injury, which is life-threatening if professional medical intervention is not obtained

S4 – Catastrophic: Directly results in death

*** Probability is defined as likelihood per 1000000 examinations*

PoH-5 – Occurs ‘every time’ ($\geq 10\,000$ per 1000000).

PoH-4 – Good chance to occur; considerable certainty to occur ($1\,000$ — $<10\,000$ per 1000000).

PoH-3 – Expected to occur from time to time; rarely occurring (100 — $<1\,000$ per 1000000).

PoH-2 – Not expected to occur (10 — <100 per 1000000).

PoH 1 – Improbable (<10 per 1000000).

There are no possible interactions with concomitant medical treatments.

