As performed routinely, an inspection bronchoscopy is performed at the start of the procedure. The selected pathway to the target lesion from the planning will be registered to and overlayed on the first performed CBCT. This overlay is visible at any time and will help the physician guide to the target lesion. If CBCT is indicated in conventional procedures, a low-dose CBCT-FluoroSweep scan will be performed of the same catheter and tool position. The CBCT-FluoroSweep has the same function as the regular CBCT, but it will be evaluated whether the low-dose CBCT-FluoroSweep is as accurate as the CBCT. Once tool-in-lesion is confirmed with either rEBUS, ROSE and/or CBCT-FluoroSweep (with regular CBCT as gold standard), tissue sampling is performed. If indicated, an EBUS is performed for staging lung cancer.

Follow-up

Safety follow-up visit will take place 1 week post-procedure (+7 days / -2 days). This visit may occur via phone or clinic visit. All adverse events that have occurred until this visit will be collected and monitored, including any prolonged hospital stay because of procedural complications, as well as unexpected complications.

[figure not shown]

Figure 3. Flowchart of the CBCT-guided navigation bronchoscopy procedure of the current clinical practice (bottom flow) and study practice with the AirWaze investigational device (top flow).

*Will be excluded from the PP population, see section 8.1.

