8.2. Sample Size Justification

A total of 37 patients will be included in this feasibility study. The physicians are familiar with the AirWaze investigational device in a non-clinical setting. The clinical setting will function as clinical and technical de-risking of the software program and the information from this study will be used to design a robust pivotal claim-driven study. Semi-structured questionnaires will be used to assess the overall system usability and the accuracy of the AirWaze CBCT-FS scan. Furthermore, the number of imaging and algorithm failures and the ability to work around quickly will be evaluated. Taking into account a 10% drop-out rate, it is expected by experts that a Per Protocol population of 33 patients is sufficient to de-risk the AirWaze features.

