8.6. Primary objective

Objective

The primary objectives of this feasibility clinical investigation are to assess the overall system usability of the Philips AirWaze investigational device (version 1.1) as measured by the System Usability Score (SUS) and the accuracy of the tool-in-lesion confirmation scan CBCT-FluoroSweep compared to the conventional CBCT.

Primary Endpoints

The system usability will be assessed by using the System Usability Scale (SUS)¹⁵. An average SUS of greater than 70 will indicate a good usability design of the AirWaze Software solution. The SUS will be measured per operator every 4 procedures that they have operated the AirWaze software solution.

Image-based tool-in-lesion confirmation accuracy of CBCT-FS is defined as the number of procedures where CBCT-FS scans were adequate to define tool-in-lesion compared to conventional CBCT scans (gold-standard). The accuracy is defined as the sum of the number of tool-in-lesion in both CBCT-FS and CBCT, and the number of no tool-in-lesion confirmation in both CBCT-FS and CBCT, divided by the total number of CBCT-FS and CBCT pairs. Image based tool-in-lesion confirmation accuracy of 90% will indicate that the CBCT-FS is postulated to be sufficient for navigation bronchoscopy.

Analysis

The results will be analyzed by using the average SUS and the SUS score development in time. No statistical test will be performed on the SUS scores due to limited data points. A SUS greater than 70 will indicate a good usability design of the AirWaze software device. More information on the SUS questionnaire can be found in Appendix I: System Usability Scale (SUS).

The results will be analyzed by calculating the overall accuracy of the CBCT-FS for tool-in-lesion confirmation. More information on the CBCT-FS scan questions can be found in Appendix II: CBCT-FS compared to CBCT. An additional analysis will be performed within the tool-in-lesion confirmation group. Tool-in-lesion scans are evaluated and subdivided into center-strike and off-center confirmation scans¹⁸, subsequently the accuracy is calculated.

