Appendix II: CBCT-FS compared to CBCT

CBCT-FluoroSweep

- What is the purpose of the CBCT-FS scan?
 - Confirm tool-in-lesion
 - Determine location of the catheter compared to the lesion
 - Other,
- If confirm tool-in-lesion purpose, can you confirm tool-in-lesion based on the CBCT-FS scan?
 - Yes, there is tool-in-lesion confirmation.
 - No, there is no tool-in-lesion confirmation.
 - Inconclusive, because
- If confirm tool-in-lesion purpose AND tool-in-lesion confirmation, is the tool-in-lesion center-strike or off-center¹⁸?
 - Center-strike
 - Off-center strike
- To what extent is the CBCT-FS imaging useful to reposition or continue (for all purposes)?

Scan	1 Not useful at all	2	3	4	5 Very useful
CBCT-FS					

- Did you notice/experience any artefacts or glitches? If yes, please elaborate.
.....

CBCT (gold-standard imaging)

- What is the purpose of the CBCT scan?
 - Confirm tool-in-lesion
 - Determine location of the catheter compared to the lesion
 - Other,
- If confirm tool-in-lesion purpose, can you confirm tool-in-lesion (in all three orthogonal orientations) based on the CBCT scan?
 - Yes, there is tool-in-lesion confirmation in all three orthogonal orientations.
 - No, there is no tool-in-lesion confirmation.
 - Maybe, the quality of the CBCT scan is not sufficient to determine tool-in-lesion confirmation.
- If confirm tool-in-lesion purpose AND tool-in-lesion confirmation, is the tool-in-lesion center-strike or off-center¹⁸?
 - Center-strike
 - Off-center
 - Lesion is too small to define center-strike or off-center*
- Did the CBCT scan change your plan based on the CBCT-FS?
 - Yes
 - No
- Did you notice/experience any artefacts or glitches? If yes, please elaborate.
.....

* The lesion size is comparable to the catheter size.

IGT Systems	Feasibility Clinical Investigation Protocol	Doc ID: XCY607-130895
	AirWaze – easy and advanced tools for CBCT guided lung interventions	Rev: 04
		Date: 2024-Jun-19
		Page 43 of 56

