The estimated radiation exposure of the AirWaze study is depicted in Table 7.

- Radiation exposure assumptions:
 - Verhoeven *et al.* has reported the radiation exposure of CBCT-guided navigation bronchoscopy for biopsy of PPNs. An average fluoroscopy time of 935 seconds was used for real-time navigation and sampling guidance. The average total DAP for these 935 seconds was 2.2 Gy·cm².
 - It is expected that the implementation of AirWaze CBCT-FS will reduce the fluoroscopy time and thus the overall DAP. This benefit of an expected reduction in fluoroscopy time is not considered in the calculations as depicted in Table 7.
- AirWaze and CBCT-FS are implemented for testing the clinical and technical feasibility. The first performed scan during a procedure is a conventional CBCT. In case additional scans are required, a CBCT-FS scan is performed on top of the conventional imaging protocol. A comparison between the additional CBCT and CBCT-FS is then made. The DAP per CBCT-FS acquisition is less than 1.45 Gy·cm² based on preclinical studies.

IGT Systems	Feasibility Clinical Investigation Protocol AirWaze – easy and advanced tools for CBCT guided lung interventions	Doc ID: XCY607-130895 Rev: 04 Date: 2024-Jun-19 Page 54 of 56
-------------	--	--

Table 7. Expected estimated radiation exposure during this Feasibility Clinical Investigation

	Low Dose Fluoroscopy		CBCT			CBCT-FS*		Total DAP (Gy·cm ²)
	DAP (Gy·cm ²)	Time (s)	Protocol	DAP (Gy·cm ²) / acq.	Acqs.	DAP (Gy·cm ²) / acq.	Acquisitions	
CBCT-NB w/o AirWaze	2.2	935	Normal dose	11.55	1	-	-	20.8-37.8
			Low dose	8.02	1-3			
Study (n=22)	2.2	935	Normal dose	11.55	1	-	-	22.3-42.2
			Low dose	8.02	1-3	1.45	1-3	

* The number of CBCT-FS scans are expected to be equal to the number of additional low dose CBCT scans performed (=total number of CBCT minus one).

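### Section 5's acquisition order conflicts with the reading order Appendix II presupposes, and no rule secures the CBCT-FS answer before the paired CBCT is seen

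*Combined protocol and SAP*

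**What the plan says.** Section 5 (Risks), in a bullet about added radiation, describes the evaluation as "combining a CBCT with immediate FluoroSweep afterwards (with the intention that they will both give similar image information". That is an acquisition order: CBCT, then CBCT-FS.

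Section 7.1 sends the accuracy endpoint to Appendix II. That form lists the CBCT-FS questions first (purpose, tool-in-lesion, centre-strike, usefulness) and the CBCT questions second. One item in the CBCT block is "Did the CBCT scan change your plan based on the CBCT-FS".

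The other places that describe the pair leave the order within it open. Section 7.4 says "a low-dose CBCT-FluoroSweep scan will be performed of the same catheter and tool position" and gives the aim: "it will be evaluated whether the low-dose CBCT-FluoroSweep is as accurate as the CBCT". Appendix VI says the first scan of a procedure is a conventional CBCT and then: "In case additional scans are required, a CBCT-FS scan is performed on top of the conventional imaging protocol".

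Section 8.6 defines accuracy as the concordant readings, positive and negative, "divided by the total number of CBCT-FS and CBCT pairs". The criterion is: "Image based tool-in-lesion confirmation accuracy of 90% will indicate that the CBCT-FS is postulated to be sufficient for navigation bronchoscopy".

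**The concern.** The endpoint is agreement between an index scan and its reference. It describes the index scan only if the index reading is made without knowledge of the reference result. Section 5 puts the CBCT in existence before the CBCT-FS. The form's question about a changed plan makes sense only if a plan was formed on the CBCT-FS before the CBCT was seen. Nothing in the visible text links the two, for example by saying that the CBCT volume is not reviewed until the CBCT-FS block is complete.

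A reader who has already seen the CBCT may resolve a doubtful or inconclusive CBCT-FS image in its favour. Agreement would then rise for a reason unrelated to CBCT-FS image quality, and the changed-plan item would lose its meaning. Section 5 also states the expectation that the two scans give similar information, which points the same way. The result is used to judge whether CBCT-FS is sufficient, and section 8.2 says the study will inform a pivotal trial.

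**Working it through.** **Side by side**

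| Place | What it fixes | What it leaves open |
|---|---|---|
| Section 5, Risks | CBCT acquired, CBCT-FS immediately after | Which volume is reviewed first |
| Appendix II | By layout and the changed-plan item, CBCT-FS read first | No instruction on when to answer, no time field, no bar on seeing the CBCT |
| Section 7.4 | Same catheter and tool position | Order of acquisition and of reading |
| Appendix VI | First scan of the procedure is a CBCT; staff probably outside the room for both scans of a pair | Order within later pairs; reading order |
| Section 7.1 | Interview based on Appendix II | When the interview takes place |
| Section 9 | Forms that may be entered directly in the e-CRF as source | Appendix II is not on the list |

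Acquisition in the section 5 order is compatible with reading in the Appendix II order under one condition: the CBCT-FS answers are recorded before the paired CBCT is reviewed. I found no text that states this condition, and no masking, answer lock, independent reader or masked re-read.

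**The plan's own figure.** Section 8.2: "Taking into account a 10% drop-out rate, it is expected by experts that a Per Protocol population of 33 patients". 33 / 0.90 = 36.7, rounded up to 37, which matches the planned total. It rests on expert opinion and says nothing about the precision of the accuracy estimate.

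**Possible size of the bias.** Let a be the agreement if the CBCT-FS is read without knowledge of the CBCT, and c the share of otherwise discordant CBCT-FS readings that follow a CBCT already seen. The documents give neither; both are assumptions.

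Expected observed agreement = a + (1 − a)c

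- a = 80%, c = 25%: 0.80 + 0.20 × 0.25 = 85%
- a = 80%, c = 50%: 0.80 + 0.20 × 0.50 = 90%
- a = 80%, c = 75%: 0.80 + 0.20 × 0.75 = 95%
- a = 75%, c = 50%: 0.75 + 0.25 × 0.50 = 87.5%

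The c at which expected agreement reaches 90% is (0.90 − a)/(1 − a): 60% for a = 75%, 50% for a = 80%, and one third for a = 85%.

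**Chance of meeting the criterion.** Table 7 expects 1 to 3 CBCT-FS scans per procedure, so 33 subjects would give about 33 to 99 pairs. There would be fewer if some scans were not made to confirm tool-in-lesion. Reading the criterion as at least 90%, 33 pairs need 30 concordant (30/33 = 90.9%; 29/33 = 87.9%). The exact binomial probability of 30 or more, treating pairs as independent, is:

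| Assumed a | c = 0 | c = 25% | c = 50% | c = 75% |
|---|---|---|---|---|
| 75% | 2.1% | 11.0% | 39.5% | 85.1% |
| 80% | 8.1% | 25.0% | 57.7% | 91.9% |
| 85% | 25.0% | 48.3% | 76.7% | 96.6% |

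With 99 pairs (90 needed) and a = 80%, the row becomes 0.3%, 6.0%, 46.4% and 97.3%. More pairs do not remove the bias: at c = 75% the chance of passing rises. Pairs within a patient or operator are correlated, so the 99-pair figures overstate precision.

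**The case against.** The strongest reply is that there is no contradiction. Section 5 is a radiation-risk statement about acquisition, while Appendix II is a reading form. Two scans taken back to back can be read in either order, and the instrument named for this endpoint already points to CBCT-FS first. Figure 3, the procedure flowchart, is not available here and may show the order. The study is a single-centre feasibility study, its conclusion is worded cautiously, and the CBCT remains the reference for every pair.

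Much of this stands. A reader might infer that the documents flatly disagree on which scan comes first; they do not, because one gives an acquisition order and the other an implied reading order. A reader might infer that one operator is stated to score both scans. The form's wording suggests it, but no text says so. A reader might also infer that agreement will be pushed past 90%. That is not shown: several assumed values in the working stay below 90%.

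What does not stand is that the form's layout is protection enough. If the CBCT is already on screen, answering the CBCT-FS block first on paper changes nothing. Even if Figure 3 gives an acquisition order, that would not control when the CBCT is reviewed.

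**Conclusion.** The point holds in a limited form. The stated acquisition order and the presupposed reading order are compatible only under a recording rule that the visible text does not contain. Following the plan as written therefore permits a CBCT-FS reading made with the CBCT result known, on a co-primary endpoint judged by a point estimate.

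The direction of any bias in such a reading is probably upward; its size is unknown. If independent agreement were 80%, half of the discordant readings would have to follow the CBCT for expected agreement to reach 90%; at 85%, one third would. At 80% with 33 independent pairs, the chance of passing runs from about 8% with no carry-over to about 92% at 75% carry-over. These are illustrations on assumed values, not estimates of what has happened in the study.

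Reading CBCT-FS first does not settle everything, because the CBCT would then be read with the CBCT-FS answer known and could drift towards it.

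**What to change.** - Reconcile sections 5, 7.4 and Appendix II on the acquisition and reading of each pair. No acquisition order is proposed here.
- State that the CBCT-FS answers for a position are recorded before the paired CBCT is reviewed, unless patient care requires earlier review. Enter the time on the Appendix II form itself, because the e-CRF audit trail would stamp only the transcription if the form is copied in later.
- Add Appendix II to the source-data list in section 9, and add a field for the reading order of each pair.
- Report accuracy for all pairs and separately for pairs read CBCT-FS first, and use the latter to interpret the 90% criterion.
- Report separately, and do not discard, pairs collected before the amendment or with unknown order. Enrolment began in October 2023 and this revision is dated June 2024, about 8 of the 18 planned months. Under uniform accrual (an assumption) that is 37 × 8/18, or roughly 16 subjects. Section 10 already calls for a before-and-after analysis if an amendment affects the integrity of the investigation.
- Acknowledge in the report that the CBCT is read with the CBCT-FS answer known.

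The cost is a protocol and form amendment, a short delay before the CBCT is reviewed, the added form entries, and fewer pairs in the order-verified analysis. It needs no extra scan, dose or patient.
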